Follow-up in the study will be summarized using the following methods to provide a comprehensive assessment of follow-up for all patients by cohort.

Summary of duration between start date of study drug and cut-off date, and follow-up times for PFS/OS/DOR, are defined as follows:

- Duration between start date of study drug and data cut-off date = (Cut-off date – Start date of study drug + 1) / 30.4375 (months).
- Follow-up time for PFS/OS = (Date of event or censoring – Start date of study drug + 1) / 30.4375 (months) regardless of censoring. Date of censoring is defined as the last adequate tumor assessment date for PFS or last contact date (when the patient is known as alive) for OS.
- Follow-up time for DOR = (Date of event or censoring – Start date of response + 1) / 30.4375 (months) regardless of censoring

Quartiles, minimum and maximum as well as the frequency count and percentage of patients in each of <1.5, 1.5-<3, 3-<6, 6-<9, 9-<12, ≥12 months will be reported for PFS, OS and DOR.

All summaries will be reported in months (see [Section 4.4](#)). The calculations for DOR and PFS will be based on BIRC assessment. Date of censoring is the same as defined for the DOR, PFS and OS analysis.

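### What the SAP calls follow-up time for PFS, OS and DOR is the endpoint time itself, so its quartiles do not measure data maturity; add reverse Kaplan-Meier follow-up and relabel the rows

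*SAP*

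**What the plan says.** SAP 2.8.1, under Duration of Follow-up, sets out several measures "to provide a comprehensive assessment of follow-up for all patients by cohort". They fall into two kinds.

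- **Start to cut-off.** "Duration between start date of study drug and data cut-off date = (Cut-off date", less the start date of study drug, plus 1, divided by 30.4375. Nothing that happens to the patient changes this value.
- **Follow-up for the endpoints.** "Follow-up time for PFS/OS = (Date of event or censoring", less the start date of study drug, plus 1, again in months. For response duration, "Follow-up time for DOR = (Date of event or censoring", counted from the start of response. Events and censored patients are pooled: "months) regardless of censoring. Date of censoring is defined as the last adequate tumor assessment date for PFS or last contact date", the last of these being for OS.

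The section then ties the dates to the endpoint analyses: "Date of censoring is the same as defined for the DOR, PFS and OS analysis". The statistics follow: "Quartiles, minimum and maximum as well as the frequency count and percentage of patients in each of" six bands from under 1.5 months to 12 months or more, for PFS, OS and DOR. Start-to-cut-off is to be summarised too, but this section does not name its statistics. No reverse Kaplan-Meier estimate is planned.

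**The concern.** A patient who dies in month 4 is placed in the 3-to-under-6-month band of OS follow-up, alongside a patient who is alive but was last contacted in month 4. The first is completely observed for OS; the second is immature data. A quartile that pools them cannot show which kind dominates, and it falls when survival is poorer.

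This matters because the study is single-arm and the final report combines cohorts enrolled at different times. SAP 2.2 pools Cohort 4 with the mutant part of Cohort 6 (N=100), and Cohort 5b with Cohort 7 (N=60). Under protocol 4.1, Cohort 6 opened only once the respective earlier cohort had completed enrolment. The Amendment 6 rationale adds Cohort 7 when 5b was already fully enrolled. A reader of the DOR, PFS and OS curves needs to know whether these groups were observed for similar lengths of time. The endpoint-based figure mixes that question with how well patients did.

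**Working it through.** **Step 1: is it the same variable as the endpoint?** The definitions in SAP 2.8.1, side by side:

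| | Clock starts | Ended by | Otherwise stops at |
|---|---|---|---|
| OS and OS follow-up | start of study drug | death | last contact |
| PFS and PFS follow-up | start of study drug | documented progression or death | last adequate tumour assessment |
| DOR and DOR follow-up | first response | documented progression or death | last adequate tumour assessment |
| Start-to-cut-off | start of study drug | nothing | cut-off date |

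The first three rows are each one variable under two names. The only difference is that the follow-up version is summarised by raw quartiles instead of Kaplan-Meier.

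**Step 2: how far apart can the measures be?** The documents give no follow-up median to reproduce. Their only figure on this point is the month length, 365.25/12 = 30.4375 days. What follows is an illustration with assumed inputs, not trial data: start-to-cut-off uniform on 30 to 66 months, exponential OS with median m, and exponential drop-out at rate d per month. For scale, the first patient was treated on 16-Jul-2015 (Amendment 2 rationale), which is 73.5 months before the 30-Aug-2021 cut-off.

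- SAP OS figure (median of the earlier of event and censoring, below 30 months): ln 2 / (ln 2/m + d). For m = 10, d = 0.005: 0.6931/(0.0693 + 0.005) = 9.3.
- Reverse Kaplan-Meier median: solve exp(-d·t) × (66 - t)/36 = 0.5. At d = 0.005, t = 43.6: 0.804 × 0.622 = 0.500.
- Start-to-cut-off median: (30 + 66)/2 = 48.

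| Monthly drop-out | SAP figure, m = 10 / 15 / 20 | Reverse KM | Reverse KM ÷ SAP figure | Start-to-cut-off minus reverse KM |
|---|---|---|---|---|
| 0.5% | 9.3 / 13.5 / 17.5 | 43.6 | 4.7 / 3.2 / 2.5 | 4.4 |
| 1% | 8.7 / 12.3 / 15.5 | 39.3 | 4.5 / 3.2 / 2.5 | 8.7 |
| 2% | 7.8 / 10.5 / 12.7 | 31.9 | 4.1 / 3.0 / 2.5 | 16.1 |

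Along each row only survival changes. The SAP figure roughly doubles at the lowest drop-out rate, while reverse Kaplan-Meier does not move.

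**Step 3: other assumed follow-up lengths.** Simulation at 0.5% monthly drop-out, with event medians of 12, 16 and 24 months:

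- Start-to-cut-off uniform on 12 to 36 months: SAP figure 11.0, 13.2, 15.7; reverse Kaplan-Meier 22.6; start-to-cut-off 24.0. Ratios 2.1, 1.7, 1.4.
- Start-to-cut-off uniform on 24 to 60 months: SAP figure 11.0, 14.3, 20.4; reverse Kaplan-Meier about 38; start-to-cut-off 42. Ratios about 3.5, 2.7, 1.9.

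So the ratio shrinks when potential follow-up is short relative to survival. The start-to-cut-off excess at 0.5% was about 1.5 to 4 months in these runs. One run with an event median of 3 months gave nearly 6 (42.0 against 36.3). Because 98% of its patients had events, very few were left to estimate the censoring curve; the exact solution of exp(-0.005t) × (60 - t)/36 = 0.5 is t = 38.2, a gap of 3.8.

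**Step 4: does the figure equal the outcome median?** Only approximately. At an event median of 6 months the raw median was 5.8, with 88 to 95% events. At 24 months with 46% events it was 15.7, against a Kaplan-Meier median of 23.9. It lies at or below the Kaplan-Meier median.

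**The case against.** The strongest reply is that the SAP already pairs two measures: "Summary of duration between start date of study drug and cut-off date, and follow-up times for PFS/OS/DOR, are defined as follows". One is unaffected by events; the other says plainly that it runs to event or censoring. A reader might infer from the second alone that the SAP has no event-free measure. The documents do not support that.

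Nor do they support saying that neither summary shows how long patients were observed. Time to death or last contact is a legitimate description of observed OS time. Reverse Kaplan-Meier answers a different question: how long patients would have been followed had no event occurred. The ratios above compare two quantities; they do not measure an error. It would also be too broad to say that progression ends all follow-up, because for OS only death does.

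Drop-out is visible elsewhere. Censoring reasons are summarised for PFS and OS (SAP 2.8.1), with loss to follow-up and consent withdrawal among the listed PFS reasons (SAP 4.6.1). Disposition is tabulated by cohort (SAP 2.5), and numbers at risk appear on the DOR plots. The larger start-to-cut-off gaps need heavy drop-out: at 2% per month, 1 - exp(-0.96) = 62% of patients still alive at 48 months would already have been lost, despite survival contact every 3 months. The unnamed statistics are also a small matter, since SAP 2.1 gives a default set for continuous data.

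All of that stands, and it keeps the point minor. What remains is the label, the lack of a maturity measure that allows for drop-out without being driven by the event rate, and DOR. DOR has no potential follow-up from first response, and its text asks for no summary of censoring reasons.

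**Conclusion.** The point holds as one of labelling and completeness, at low severity. The PFS, OS and DOR follow-up times are endpoint times and should not be read as maturity. Start-to-cut-off is a fair upper description of follow-up from first dose, close to reverse Kaplan-Meier when few patients are lost, and too long when many are.

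The sizes are illustrative. The SAP's OS figure is about 2.5 to 5 times shorter than reverse Kaplan-Meier under the 30-to-66-month assumptions, and as little as 1.4 times shorter with 12 to 36 months and an event median of 24. At 0.5% monthly drop-out, start-to-cut-off is about 1.5 to 4.5 months longer than reverse Kaplan-Meier, apart from the unstable simulated gap of nearly 6; it is more only at higher drop-out. The documents give no drop-out rate. No planned analysis is triggered by these summaries.

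**What to change.** In SAP 2.8.1, Duration of Follow-up:

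1. Add reverse Kaplan-Meier follow-up (events treated as censored, censoring treated as the event) for OS, PFS and DOR, with median and quartiles, by cohort and by the combined cohorts of SAP 2.2. For DOR the clock starts at first response.
2. Keep the event-or-censoring summary, relabelled as observed time to event or censoring.
3. Keep start-to-cut-off, labelled as potential follow-up, and name its statistics.

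Show the number censored beside each reverse Kaplan-Meier median, because the estimate is unstable when nearly all patients have had the event. The cost is one SAP paragraph, the PROC LIFETEST code in SAP 4.6.3 rerun with the censoring indicator swapped, and a few table rows. No new data are needed.

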2.8.2 Safety

All safety analyses will be performed based on the Safety Set by cohort and also for all patients. Safety will also be presented combining the MET mutant cohorts and amplified cohorts as defined in [Section 2.2](#).

Baseline

Baseline is the result of an investigation describing the “true” uninfluenced state of the patient. The last available assessment before or on the start date of study drug is defined as “baseline” value or “baseline” assessment. If an assessment is planned to be performed prior to the first dose of study drug in the protocol and the assessment is performed on the same day as the first administration of study drug, it will be assumed that it was performed prior to study drug administration, if assessment time point is not collected or is missing. If assessment time points are collected, the observed time point will be used to determine pre-dose on study day 1 for baseline calculation. Unscheduled assessments will be used in the determination of baseline. See [Section 4.7.2](#) for further details on derivation of baseline for laboratory data and ECGs.

Patients who start treatment and discontinue from the study on the same day may have 2 different sets of data collected on study day 1, one being reported to the cycle 1 day 1 visit, the other reported to the end of treatment (EOT) visit. Data reported at the EOT visit are not eligible for baseline selection.

Grouping for the analyses

The overall observation period will be divided into three mutually exclusive segments:

- Pre-treatment period: from day of patient’s informed consent to the day before first dose of study drug
- On-treatment period:
 - For discontinued patients, from day of first dose of study drug to 30 days after last dose of study drug
 - For ongoing patients, from day of first dose of study drug to the data cut-off date
- Post-treatment period: starting at day 31 after last dose of study drug

The safety summary tables will include only assessments collected no later than 30 days after study drug discontinuation and assessments prior to the data cut-off date for on-going patients, unless otherwise specified.

For select items, shift tables or change from baseline summaries generated for laboratory, ECG, vital signs and change score generation may use data from pre-treatment period for baseline calculations.

All data, regardless of observation period, will be listed and assessments collected in the post-treatment period will be flagged in all the listings.

Adverse events (AEs)

AEs will be coded using MedDRA using the latest version available prior to clinical database lock and will be graded using Common Terminology Criteria for Adverse Events (CTCAE) version 4.03. If CTCAE grading does not exist for an AE, grades 1, 2, 3, or 4 corresponding to the severity of mild, moderate, severe, and life-threatening, respectively, will be used. CTCAE grade 5 (death) will not be used in this study; rather, this information will be collected on the fatal outcome from “Adverse event”, “End of Treatment Phase completion”, “End of post-treatment phase Completion” or “Death” eCRF pages.

All AE summaries will be summarized (frequency counts and percentages) by system organ class and/or preferred term, and maximum severity grades, except where otherwise noted. A patient with multiple CTC grades for an AE will be summarized under the maximum CTC grade recorded for the event.

The following AE summaries will be produced:

- AEs regardless of study drug relationship
- AEs suspected to be study drug related
- On-treatment deaths, by primary system organ class and preferred term
- All deaths, by primary system organ class and preferred term
- SAEs regardless of study drug relationship
- SAEs suspected to be study drug related
- AEs leading to permanent discontinuation of study drug regardless of study drug relationship
- AEs leading to permanent discontinuation of study drug suspected to be study drug related
- AEs requiring dose adjustment and/or study drug interruption regardless of study drug relationship
- AEs requiring dose adjustment and/or study drug interruption suspected to be study drug related
- AEs requiring dose adjustment regardless of study drug relationship
- AEs requiring dose adjustment suspected to be study drug related
- AEs requiring study drug interruption regardless of study drug relationship
- AEs requiring study drug interruption suspected to be study drug related
- AEs requiring significant additional therapy regardless of study drug relationship
- AEs requiring significant additional therapy suspected to be study drug related
- Non-SAEs (AEs excluding SAEs) regardless of study drug relationship

In addition, a summary of serious adverse events with number of occurrences will be produced (an occurrence is defined as >1 day between start and prior end date of record of same preferred term).

A listing will be provided to document any terms changed as a result of the re-mapping process to the latest MedDRA version available.

All AEs regardless of study drug relationship and all AEs suspected to be study drug related will be summarized by cohort and subgroup (as described in [Section 2.2](#)) using the safety set.

Exposure-adjusted overall incidence

The number and percentage of patients with any AEs along with the 95% confidence interval (95% CI) will be presented [[Clopper and Pearson 1934](#)]. In order to account for potential differences in exposure across groups, incidence rates of adverse events will be presented adjusted for Subject-Months exposure. [[Sahai and Khurshid, 1993](#); [Ulm 1990](#)].

The exposure-adjusted overall incidence rate is defined as the number of patients with an event divided by the corresponding sum of the exposure duration for all patients, where duration of exposure in Subject-Months is counted up to the first qualifying event (or end of time at risk for patients without event). AEs missing start date for exposure-adjusted overall incidence calculation is handled as follows: Start date of study drug will be considered as the AE start date for any AE with missing start date.

Adverse events of special interest

An adverse event of special interest is a grouping of adverse events that are of scientific and medical concern specific to compound INC280. These groupings are defined using MedDRA terms, SMQs (standardized MedDRA queries), HLGTs (high level group terms), HLT (high level terms) and PTs (preferred terms). Customized SMQs (Novartis MedDRA queries, NMQ) may also be used. A NMQ is a customized group of search terms which defines a medical concept for which there is no official SMQ available or the available SMQ does not completely fit the need. It may include a combination of single terms and/or an existing SMQ, narrow or broad.

All AESI definitions or AE grouping are specified in the electronic Case Retrieval Strategy (eCRS), in which they are identified by the flag “SP”. Additional AESI may be reported if there are any updates to the eCRS at the time of the analyses.

Adverse events of special interest (AESIs) INC280 are:

- Hepatotoxicity
- Renal dysfunction
- ILD/Pneumonitis
- Central nervous system toxicity
- Pancreatitis
- Photosensitivity
- Teratogenicity
- Drug-drug interactions with strong CYP3A4 inducers
- QTc interval prolongation

This classification reflects the current version of the eCRS and might be updated based on review of accumulating data.

For each specified AESI, number and percentage of patients with at least one event of the AESI occurring during on treatment period will be summarized.

Summaries of these AESIs will be provided by cohort, (specifying grade, SAE, relationship, leading to permanent treatment discontinuation, leading to dose adjustment/interruption, death, etc.).

Analysis of time to first occurrence of any grade AESI will be applied as well as time to first occurrence of grade 3/4 AESI using the Kaplan-Meier method (see below the definitions). Duration of first occurrence of grade 3/4 AESI will also be summarized. These analyses will be performed for AESI regardless of study drug relationship and for AESI suspected to be study drug related.

For time to first occurrence, failure curves (ascending Kaplan-Meier curves) will be constructed in the combined MET mutant cohorts and all patients. Median together with 95% CI as well as 25th and 75th percentiles will be presented. In addition, the median time to occurrence for the subset of patients who experienced the event of interest will be calculated. Simple descriptive statistics (median, min and max, 25th and 75th percentiles) will be presented. The probabilities at selected time points and the associate 95% CI will also be summarized.

Duration of first occurrence of grade 3/4 AESI will be presented for the subset of patients who experienced the event. Failure curves (ascending Kaplan-Meier curves) will be constructed in the combined MET mutant cohorts and all patients. Median together with 95% CI as well as 25th and 75th percentiles will be presented.

Duration of first occurrence of an event will be presented for the subset of patients of the safety set who experienced the event. A patient will be censored for time to resolution, if there is no resolution during the on-treatment period. The same censoring rules as described below for time to first occurrence apply.

Time to first occurrence

- Time to first occurrence of an event is defined as time from start of study treatment to the date of first occurrence of this event (or first event within an AE grouping), i.e. time in days is calculated as (start date of first occurrence of event) – (start of study treatment) +1.
- In the absence of an event during the on-treatment period, the censoring date applied will be the earliest of the following dates: death date, new anti-neoplastic antineoplastic therapy start date, end date of on-treatment, analysis cut-off date, and withdrawal of informed consent date. See [Section 2.7.1](#) for the definition of new anti-neoplastic antineoplastic therapy.

Duration of first occurrence (i.e. Time to resolution of an event)

- Duration of first occurrence of an event is defined as time from onset to the date of resolution of the first event: (date of resolution of first event) – (date of onset of event) + 1.
- Resolution of the event means that outcome of the Grade 3/4 event is “recovered/resolved”, “recovered/resolved with sequelae”, or “recovering/resolving” (returning to grade ≤ 2). The same preferred term as the 1st event identified is used to determine the resolution. The resolution occurring after end of treatment + 30 days will be considered.
- The date of resolution of first Grade 3/4 event is derived as follows:
 - = End date of the first Grade 3/4 event *if the first event is resolved* (i.e. duration of AE). If multiple Grade 3/4 events with the same start date are reported, the latest end date will be considered (i.e. the longest duration of AE).
 - = Start date of the 1st Grade ≤ 2 event *if the first event is improved*. If multiple Grade 3/4 events with the same start date are reported, the latest start date of the

1st Grade \leq 2 event will be considered (i.e. the longest duration of first occurrence).

- = Start date of the 1st Grade \leq 2 event *if the first event is worsened and then improved*, and no Grade 3/4 AE with an outcome “resolved/recovered” reported later on. If multiple Grade 3/4 events with the same start date are reported, the latest start date of the 1st Grade \leq 2 event will be considered (i.e. the longest duration of first occurrence).
- = End date of the Grade 3/4 event reported with outcome “recovered/resolved” *if the first event is worsened and then resolved* and Grade 3/4 AE with an outcome “resolved/recovered” reported.

With

- *Worsened: Event with a non-missing end date and outcome “not recovered/ not resolved”*
- *Improved: Event with a non-missing end date and outcome “recovering/not resolving”. Event with a lower grade are expected to be reported*
- *Resolved: Event with a non-missing end date and outcome “recovered/ not resolved” or “resolved/resolved with sequelae”*

[Section 4.7.4](#) provides further details on the definition of first occurrence and duration.

Deaths

Separate summaries for on-treatment and all deaths will be produced by cohort, primary system organ class and preferred term.

All deaths will be listed, post treatment deaths will be flagged.

Laboratory data

For laboratory data assessments, data from all sources (central and local laboratories) will be combined. The summaries will include all laboratory assessments collected no later than 30 days after study drug discontinuation. All laboratory assessments will be listed and those collected later than 30 days after study drug discontinuation will be flagged in the listings.

Laboratory data will be classified (by Novartis Oncology Statistical Programming) into CTC grades according to the NCI CTCAE v4.03. For all reports, CTC grade is always obtained on the converted measurement in SI unit. Grade 5 will not be used. The CTC grade 0 will be assigned as below in different scenarios:

- For lab parameters defined by criteria based on normal range only, a severity grade of 0 will be assigned when the value is within normal limits.
- For lab parameters whose grade is defined by criteria based on normal range and absolute values (e.g. platelet count decrease). A severity grade of 0 will be assigned when the value is within normal limits.

- For lab parameters whose grade is defined by criteria based on normal range and the change from baseline value, with no other associated clinical criteria such as concomitant medication (e.g. creatinine increased) the following will be applied. For the baseline grading and for the grading of post-baseline lab values with missing baseline grading, the grade will be derived using the criteria based only on the normal range as per CTCAE v4.03. A severity grade of 0 will be assigned when the post-baseline value is \leq ULN (for hyper) or \geq LLN (for hypo).

Parameters for which a grading does not exist will be classified into low/normal/high group by means of laboratory normal ranges.

The following summaries will be produced by cohort for the hematology and biochemistry laboratory data (by laboratory parameter):

- Shift tables using CTC grades to compare baseline to the worst post-baseline value for laboratory parameters with CTC grades
- Shift tables using low, normal, high (as well as low and high combined) classifications to compare baseline to the worst post-baseline value for laboratory parameters where CTC grades are not defined.
- New or worsened abnormalities for laboratory parameters based on CTC grade
- Trends of renal function parameters (creatinine, BUN) over time (baseline and selected on-treatment time-points, See [Table 4-6](#)) will be displayed via boxplots based on time windows and corresponding tables displaying the statistics used for the box plots by the selected time points.

The following lab parameters will be summarized by cohort:

- Hematology: absolute lymphocytes, absolute neutrophils, hemoglobin (anemia), WBC, platelet counts, absolute basophils, absolute eosinophils, absolute monocytes, hematocrit
- Biochemistry: alkaline phosphatase (ALP), SGPT (ALT), SGOT (AST), total bilirubin, amylase, potassium, sodium, creatinine, glucose (hypo only), phosphate, albumin, calcium, magnesium, creatinine, direct bilirubin, blood urea nitrogen (BUN), GGT, lipase.
- For bi-directional parameters, both hyper and hypo summaries will be presented.

The following laboratory parameters will be presented in listings and will not be summarized:

- Urinalysis: macroscopic panel (dipstick) (bilirubin, blood, glucose, WBC, pH, protein, specific gravity), Urinalysis Microscopic panel (RBC, WBC, casts).
- Coagulation: INR, pro-thrombin time (PT) or Quick Test

The following listings will be produced for the laboratory data for all laboratory parameters where CTC grades are defined:

- Listing of patients with laboratory abnormalities of CTC grade 3 or 4
- Listing of all laboratory data with values flagged to show the corresponding CTC grades and the classifications relative to the laboratory reference ranges.

Liver function parameters of interest are total bilirubin (TBIL), ALT, AST and alkaline phosphatase (ALP). The number (%) of patients with worst post-baseline values will be summarized by cohort in the following categories:

- ALT >3×ULN, >5×ULN, >8×ULN, >10×ULN, >20×ULN
- AST >3×ULN, >5×ULN, >8×ULN, >10×ULN, >20×ULN
- ALT or AST >3×ULN, >5×ULN, >8×ULN, >10×ULN, >20×ULN
- TBIL > 2×ULN, >3×ULN

Combined and concurrent values post-baseline

- ALT or AST > 3×ULN & TBIL > 2×ULN
- ALT or AST > 3×ULN & TBIL > 2×ULN & ALP \geq 2×ULN
- ALT or AST > 3×ULN & TBIL > 2×ULN & ALP < 2×ULN

Combined elevations values post-baseline (regardless of baseline levels)

- ALT or AST > 3×ULN & TBIL > 2×ULN
- ALT or AST > 3×ULN & TBIL > 2×ULN & ALP \geq 2×ULN
- ALT or AST > 3×ULN & TBIL > 2×ULN & ALP < 2×ULN

Combined elevations values post-baseline by baseline levels

AST/ALT \leq ULN at baseline

- ALT or AST > 3×ULN & TBIL > 2×ULN
- ALT or AST > 3×ULN & TBIL > 2×ULN & ALP \geq 2×ULN
- ALT or AST > 3×ULN & TBIL > 2×ULN & ALP < 2×ULN

AST/ALT > UNL at baseline

- Elevated ALT or AST & TBIL (>2×Baseline and 2×ULN)
- Elevated ALT or AST & TBIL (>2×Baseline and 2×ULN) & ALP \geq 2×ULN
- Elevated ALT or AST & TBIL (>2×Baseline and 2×ULN) & ALP < 2×ULN

with Elevated AST or ALT defined as: >3×ULN if \leq ULN at baseline, or (>3×Baseline or 8×ULN) if > ULN at baseline

In addition, a listing of all TBIL, ALT, AST and ALP values for patients with a post-baseline TBIL > 2×ULN, ALT > 3×ULN or AST > 3×ULN will be provided.

The relationship between post-baseline increases in ALT/AST and total bilirubin will be shown using eDISH plot: peak values of Total bilirubin vs peak values of ALT/AST at any time during the course of treatment (not necessarily concurrent).

Analysis of time to first occurrence of grade 3/4 AST/ALT (whichever occurs first) will be done. Time to first occurrence of grade 3/4 AST/ALT and duration of the first occurrence of grade 3/4 AST/ALT will be summarized using Kaplan-Meier method. Patients with grade 3/4 AST/ALT at baseline will be excluded from the analysis. Median together with 95% CI as well as 25th and 75th percentiles will be presented. In addition, the median time to occurrence for the subset of patients who experienced the event of interest will be calculated. Simple descriptive statistics

(median, min and max, 25th and 75th percentiles) will be presented. The probabilities at selected time points and the associate 95% CI will also be summarized.

Duration of first occurrence of grade 3/4 AST/ALT will be presented for the subset of patients who experienced the event. Median together with 95% CI as well as 25th and 75th percentiles will be presented.

ECGs

ECG data will be analyzed based on central laboratory reported results by cohort. The summaries will include all ECG assessments performed no later than 30 days after the last date of study drug. All ECG assessments will be listed, and those collected later than 30 days after study drug discontinuation will be flagged in the listing.

The number and percentage of patients with notable ECG values will be presented by cohort.

- QTcF and QTcB
 - New value of > 450 and \leq 480 ms
 - New value of > 480 and \leq 500 ms
 - New value of > 500 ms
 - Increase from Baseline of > 30 ms to \leq 60ms
 - Increase from Baseline of > 60 ms
- HR
 - Increase from baseline >25% and to a value > 100 bpm
 - Decrease from baseline >25% and to a value < 50 bpm
- PR
 - Increase from baseline >25% and to a value > 200 ms
 - New value of > 200 ms
- QRS
 - Increase from baseline >25% and to a value > 120 ms
 - New value of > 120 ms

In addition the following analysis will be carried out;

- Descriptive statistical analysis (mean and two-sided 90% confidence interval) by time point of assessment for Δ QTcF (QTcF change from baseline).
- A graphical presentation of ECG mean change from baseline over time will be produced based on time windows.
- Shift table based on notable values to compare baseline to the worst post-baseline value for QT, QTcF and QTcB.
- Summary of newly occurring post-baseline qualitative ECG abnormalities.

Vital signs

Vital sign assessments will be performed in order to characterize basic body function. The parameters collected are weight (kg), body temperature (°C), pulse rate (beats per minute) and systolic and diastolic blood pressure (mmHg).

Clinically notable elevated values are defined as:

- Systolic BP: ≥ 180 mmHg and an increase ≥ 20 mmHg from baseline
- Diastolic BP: ≥ 105 mmHg and an increase ≥ 15 mmHg from baseline.
- Body temperature: $\geq 39.1^{\circ}\text{C}$
- Weight: increase from baseline of $\geq 10\%$
- Pulse rate: ≥ 100 bpm with increase from baseline of $\geq 25\%$

Clinically notable below normal values are defined as:

- Systolic BP: ≤ 90 mmHg and a decrease ≥ 20 mmHg from baseline
- Diastolic BP: ≤ 50 mmHg and a decrease ≥ 15 mmHg from baseline
- Body temperature: $\leq 35^{\circ}\text{C}$
- Weight: decrease from baseline of $\geq 10\%$
- Pulse rate: ≤ 50 bpm with decrease from baseline of $\geq 25\%$

Vital signs shift table based on values classified as notable low, normal, notable high or notable (high and low) at baseline and worst post-baseline will be produced for pulse rate, diastolic BP and systolic BP.

Baseline values (Low/high) are defined as:

- Systolic BP: ≤ 90 mmHg ; Systolic BP: ≥ 180 mmHg
- Diastolic BP: ≥ 105 mmHg ; Diastolic BP: ≤ 50 mmHg
- Body temperature: $\leq 35^{\circ}\text{C}$; Body temperature: $\geq 39.1^{\circ}\text{C}$
- Pulse rate: ≤ 50 bpm ; Pulse rate: ≥ 100 bpm

Patients with clinically notable vital sign abnormalities will be listed. All vital sign assessments will be listed by patient and vital sign parameter by cohort.

In the listings, clinically notable values will also be flagged.

[figure not shown]
ECOG performance status

The ECOG performance status assessment allows patients to be classified as to their functional impairment, the definition of scores in relation to their performance status is provided in [Table 2-2](#), ranging from 0 (most active) to 5 (dead):

Table 2-2 ECOG performance scale

Score	Description
0	Fully active, able to carry on all pre-disease performance without restriction
1	Restricted in physically strenuous activity but ambulatory and able to carry out work of a light or sedentary nature, e.g., light house work, office work
2	Ambulatory and capable of all self-care but unable to carry out any work activities. Up and about more than 50% of waking hours
3	Capable of only limited self-care, confined to bed or chair more than 50% of waking hours
4	Completely disabled. Cannot carry on any self-care. Totally confined to bed or chair
5	Dead

Shift tables of ECOG performance status at baseline to worst post-baseline ECOG performance status by score will be provided by cohort using the safety set; shift tables of ECOG performance status at baseline to best post-baseline ECOG performance status by score will also be provided. ECOG performance status at each time point will be listed by cohort.

